9.2.2. SARS-COV-2 Pandemic

The first known case of SARS-CoV-2 infection in the US is thought to have occurred in the US in late January 2020. Testing to detect SARS-CoV-2 infection in the US began in late February 2020. Due to limited number of tests available, testing was extremely limited and selective throughout February until early March 2020. In March, CDC removed certain restrictions on who could perform and receive the tests. In April 2020 antibody testing became widely available but difficult to interpret. This study will include patients identified at the beginning of the emergence of the SARS-CoV-2 pandemic in the US, when diagnostic tests were limited and of varying reliability, access to care was potentially restricted, and availability and standards of treatment were evolving. The study will continue over two years during which testing availability, reliability and recommendations, case contact tracing, and treatment will evolve.

With respect to testing, as of 22 April 2020 the following CDC guidelines, initially proposed on 19 March 2020, were still in place (https://www.coronavirus.gov/):

"Clinicians should use their judgment to determine if a patient has signs and symptoms compatible with COVID-19 and whether the patient should be tested. Most patients with

^[1] 45 CFR 164.514(b)(1).

^[2] Guidance Regarding Methods for De-identification of Protected Health Information in Accordance with the Health Information Insurance Portability and Accountability Act (HIPAA) Privacy Rule (Dated as September 4, 2012, as first released on November 26, 2012).

confirmed COVID-19 have developed fever and/or symptoms of acute respiratory illness (eg, cough, difficulty breathing)."

The CDC assigned priorities for who should be tested:

Priority 1:

- Hospitalized patients;
- Healthcare facility workers with symptoms.

Priority 2:

- Patients in long-term care facilities with symptoms;
- Patients 65 years of age and older with symptoms;
- Patients with underlying conditions with symptoms;
- First responders with symptoms.

Priority 3:

- Critical infrastructure workers with symptoms;
- Individuals who do not meet any of the above categories with symptoms;
- Healthcare facility workers and first responders;
- Individuals with mild symptoms in communities experiencing high numbers of COVID-19 hospitalizations.

Nonpriority:

• Individuals without symptoms.

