CDC provided additional guidance that state and local guidelines should adapt these recommendations to reflect potentially rapidly changing local circumstances.

In the US approximately 10,000 SARS-CoV-2 infection tests had been conducted by March 12 with roughly 2,200 testing positive. By April 1, nearly 1.2 million tests had been performed with 215,329 positives. By 22 April 2020 over 4.4 million tests had been performed with 826,936 positive tests (Note: Two tests are recommended to be performed on the same individual so this is not an estimate of affected persons) (The COVID Tracking Project).² As of 22 April 2020 SARS-CoV-2 infection testing is largely limited to patients who are symptomatic.

As of April 22, there is a lack of universal SARS-CoV-2 infection or antibody screening therefore, no US data exist that would allow for the study of asymptomatic infected persons, the true rate of SARS-CoV-2 infection, or rates of COVID-19 illness among SARS-CoV-2-infected persons.

Patients with chronic conditions, such as those treated with tofacitinib, may have different rates of infection from the general population for a variety of reasons. For example, the condition or its treatment may be associated with higher risk of infections generally, thus, patients and their HCP may take extra precautions to avoid exposure to the virus. On the other hand, patients may be more likely to be referred for testing and therefore diagnosed if they are perceived to be at higher risk of infection or of more serious clinical course of infection. However, within an indicated population, patient characteristics or prescribed treatment regimens are not likely to determine probability of referral for testing, barring an association with symptomatic disease. Thus, understanding the course of disease in patients with confirmed SARS-CoV-2 infection will inform our understanding of how different conditions, patient characteristics, and treatments impact the course of SARS-CoV-2 in a population known to be infected.

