9.2.4. Exclusion Criteria

There are no exclusion criteria for this study.

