9.3. Variables

Variable	Role	Operational definition ^a
SARS-CoV-2 Diagnosis	Inclusion criteria	SARS-CoV-2 diagnosis.
Rheumatoid Arthritis	Subcohort identification	RA diagnosis in baseline period.
Psoriatic Arthritis	Subcohort identification	PsA diagnosis in baseline period.
Ulcerative Colitis	Subcohort identification	UC diagnosis in baseline period.
Non-indicated subcohort	Inclusion criteria/Subcohort identification	Absence of RA, PsA, and UC codes within baseline period.
SARS-CoV-2 Diagnosis Date	Exposure/Index date	Date associated with SARS-CoV-2 diagnosis.
Baseline systemic therapy	Baseline Characteristic/Exposure	Evidence of therapy prescribed 6 months prior to index date.
		Categorical: csDMARD, TNFi, non- TNFi, tofacitinib, JAK inhibitor (as monotherapy or combination therapy).
Baseline csDMARD	Baseline Characteristic/Exposure (Comedication)	Evidence of therapy prescribed within 6 months prior to index date.
Baseline TNFi	Baseline Characteristic/Exposure	Evidence of therapy prescribed within 6 months prior to index date.
Baseline Non-TNFi	Baseline Characteristic/Exposure	Evidence of therapy prescribed within 6 months prior to index date.
Baseline bDMARD	Baseline Characteristic/Exposure	TNFi or non-TNFi prescribed within 6 months prior to index date.
Baseline tofacitinib	Baseline characteristic/Exposure	Tofacitinib Evidence of therapy prescribed within 6 months prior to index date.
Baseline JAK inhibitor	Baseline Characteristic/Exposure	Evidence of therapy prescribed within 6 months prior to index date.
Baseline Monotherapy	Baseline characteristic/Exposure	No evidence of MTX or other csDMARD concomitant with baseline advanced systemic therapy (ie, TNFi, non-TNFi, tofacitinib, JAK inhibitor).
Baseline Combination therapy	Baseline characteristic/Exposure	Evidence of MTX or other csDMARD concomitant with baseline advanced systemic therapy (ie, tofacitinib, bDMARD, JAK inhibitor, csDMARD) and MTX or other csDMARD.

Variable	Role	Operational definition ^a
Post-SARS systemic therapy	Baseline Characteristic/Exposure	Evidence of therapy prescribed within 6 months after index date.
		Categorical: csDMARD, TNFi, non-TNFi, tofacitinib, JAK inhibitor (as monotherapy or combination therapy).
Post-SARS csDMARD	Baseline Characteristic/Exposure (Comedication)	Evidence of therapy prescribed within 6 months on or after index date.
Post-SARS TNFi	Baseline Characteristic/Exposure	Evidence of therapy prescribed within 6 months on or after index date.

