CKD/Dialysis	Risk factor	Diagnosis of CKD or dialysis procedure within 6 month baseline period.
Liver Disease	Risk factor	Diagnosis of liver disease within 6 month during baseline period.
Corticosteroid Use	Risk factor	Evidence of use within 6 month baseline period.
SARS diagnosis site	Endpoint	Facility location where SARS-CoV-2 was diagnosed (eg, ER, ICU, outpatient).
Hospitalization	Primary Endpoint	Yes/No: hospitalization within 30 days post-SARS-CoV-2 diagnosis.

Variable	Role	Operational definition ^a
ICU admission	Primary Endpoint	Yes/No admission to ICU within 30 days post-SARS-CoV-2 diagnosis.
In hospital death	Endpoint	Discharge diagnosis = death post hospitalization associated with SARS-CoV-2 diagnosis.
All-cause mortality	Endpoint	Death within 90 days post-SARS-CoV-2 infection.
Length of hospital stay	Endpoint	Duration of inpatient stay for visit associated with SARS-CoV-2 diagnosis.
Length of ICU stay	Endpoint	Duration of ICU stay for visit associated with SARS-CoV-2 diagnosis.
Respiratory failure	Endpoint	Diagnosis in conjunction with SARS-CoV-2 diagnosis.
Kidney failure	Endpoint	Diagnosis in conjunction with SARS-CoV-2 diagnosis.
Thrombosis/coagulation events/stroke	Endpoint	Diagnosis in conjunction with SARS-CoV-2 diagnosis.
ARDS	Endpoint	Diagnosis in conjunction with SARS-CoV-2 diagnosis.
Heart failure	Endpoint	Diagnosis in conjunction with SARS-CoV-2 diagnosis.
Sepsis/septic shock	Endpoint	Diagnosis in conjunction with SARS-CoV-2 diagnosis.
Invasive ventilation	Endpoint	Procedure performed during hospitalization associated with SARS-CoV-2 diagnosis.
Non-invasive ventilation	Endpoint	Procedure performed during hospitalization associated with SARS-CoV-2 diagnosis.
ЕСМО	Endpoint	Procedure performed during hospitalization associated with SARS-CoV-2.
Oxygen therapy	Endpoint	Procedure performed during hospitalization associated with SARS-CoV-2 diagnosis.
IV immunoglobulin	Endpoint	Procedure performed during hospitalization associated with SARS-CoV-2 diagnosis.

Variable	Role	Operational definition ^a
Discharge Disposition		Disposition at discharge from hospital stay associated with SARS-CoV-2 diagnosis.

a. Where applicable codes and other definitions to be further defined in Statistical Analysis Plan.

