9.7. Data Analysis

After selection of the study population, summary statistics of baseline variables will be determined for the baseline period. The index date for each patient is defined as the first date that the study inclusion criteria are satisfied. Baseline variables will be summarized as

appropriate for categorical and continuous variables with 95% CI provided to show precision of the estimate.

Among patients who are included in the study, outcomes will be included that occur during the risk window from index date until the first of death (based on discharge status), 3 months post-SARS-CoV-2 diagnosis, or end of study period/datacut.

The endpoints of interest within each indication, non-indicated subcohort and indication/treatment combination will be summarized as appropriate for categorical and continuous variables with 95% CI provided to show precision of the estimate.

The handling of missing data will be described in the SAP. No variables will be imputed.

Detailed methodology for summary and statistical analyses of data collected in this study will be documented in a Statistical Analysis Plan (SAP), which will be dated, filed and maintained by the sponsor. The SAP may modify the plans outlined in the protocol; any major modifications of primary endpoint definitions or their analyses would be reflected in a protocol amendment.

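### Read literally, the ICU primary endpoint scores as No a patient already in ICU at diagnosis and not readmitted there; the hospitalization endpoint is ambiguous on the same point

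*Protocol*

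**What the plan says.** The variables table in Protocol Section 9.3 names two primary endpoints. ICU admission is "Yes/No admission to ICU within 30 days post-SARS-CoV-2 diagnosis". Hospitalization is "Yes/No: hospitalization within 30 days post-SARS-CoV-2 diagnosis". The index date is the "Date associated with SARS-CoV-2 diagnosis". Section 9.7 adds that "outcomes will be included that occur during the risk window from index date until the first of death", with later cut-offs at 3 months and at the end of the study period or data cut.

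The protocol foresees patients who are already in hospital when diagnosed:
- The diagnosis-site variable in Section 9.3 is the "Facility location where SARS-CoV-2 was diagnosed (eg, ER, ICU, outpatient"). It is listed as an endpoint.
- Section 9.2.2 puts "Hospitalized patients" in the first testing priority, together with symptomatic healthcare facility workers.
- Section 9.2.4 states: "There are no exclusion criteria for this study".

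The other inpatient endpoints in the same table are anchored differently. Length of hospital stay, length of ICU stay, invasive and non-invasive ventilation, ECMO and in-hospital death all refer to the visit or hospitalization linked to the diagnosis, whenever that stay began.

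A footnote to the table leaves codes and further definitions to the SAP. Section 9.7 lets the SAP modify the plan, but requires a protocol amendment for major changes to primary endpoint definitions.

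**The concern.** A patient diagnosed in the ICU a few days after entering it has the outcome that the ICU endpoint is meant to capture. On the literal wording, that patient has no qualifying admission. The same patient can then have an ICU length of stay, a ventilation record and an in-hospital death alongside a No for ICU admission, so the tables would not agree with each other.

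The loss need not be equal across groups. Section 9.1 says the study seeks to understand whether manifestations differ by treatment or by indication. If one stratum is diagnosed more often during a stay already under way, its primary endpoint falls for that reason alone. The mix may also shift over time, because Section 9.2.2 expects testing to evolve over the study.

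Counting these stays does not settle everything. Where admission came before diagnosis it may have prompted the test, and the proportion is then not a risk following diagnosis.

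A related problem affects the baseline. Days hospitalized, and hospitalized infection or parenteral antibiotic use, are taken over the 6 months before index with no stated carve-out for the index admission. The days of that admission before diagnosis can therefore be recorded as prior history and used as potential confounders.

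**Working it through.** The protocol states no event rate, sample size or share diagnosed as inpatients, so there is no figure to reproduce. The check has two parts.

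**1. How the wording scores four cases (Sections 9.3 and 9.7)**

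| Case | ICU admission | Hospitalization | Stay-linked endpoints |
|---|---|---|---|
| Admitted to ICU on the index date | Yes (window opens that day) | Yes | Counted |
| On a ward at diagnosis, moved to ICU within 30 days | Yes | Unclear | Counted |
| In ICU since before the index date, no ICU readmission | No, read literally | Unclear | Counted |
| On a ward since before the index date, never in ICU | No, correctly | Unclear | Counted |

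The third row is the miscount for ICU. Hospitalization is unclear in the last three rows because its definition names hospitalization, not admission. Being in hospital during the window could satisfy it, or a new admission could be required.

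**2. Illustrative size. All inputs are assumptions.**

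Let R be the inclusive risk (stay open at index or starting within 30 days), s the share of those events whose stay began before the index date, and r the share of that group with a new admission in the window.

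Reported risk = R × (1 − s × (1 − r)).

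With R = 20% and r = 0:
- s = 20%: 0.20 × 0.80 = 16%
- s = 40%: 0.20 × 0.60 = 12%
- s = 60%: 0.20 × 0.40 = 8%

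With r = 15%, the three values become 0.20 × 0.83 = 16.6%, 0.20 × 0.66 = 13.2% and 0.20 × 0.49 = 9.8%.

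The same relation can be written with g, the share of the cohort admitted on or after index, and f, the share already in at index. The fraction of inclusive events captured is (g + f × r) / (g + f).
- Hospitalization, if read as new admission only, with g from 5% to 20%, f from 2% to 20% and r of 0 or 15%: from 0.05 / 0.25 = 20% to (0.20 + 0.02 × 0.15) / 0.22 = 92%.
- ICU, with g of 2% or 5%, f from 0.5% to 5% and r = 0: from 0.02 / 0.07 = 29% to 0.05 / 0.055 = 91%.

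For a comparison of strata, take two groups with the same inclusive risk of 20% and r = 0, with 5% and 10% of patients already in at diagnosis. The new-admission reading gives 20% − 5% = 15% and 20% − 10% = 10%, a ratio of 0.10 / 0.15 = 0.67 where the inclusive risks are equal.

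**The case against.** The strongest reply is that this is a wording gap that the SAP may close. The protocol leaves codes and further definitions to the SAP, and Section 9.2.3 leaves the diagnosis definition and baseline period to it as well. If the index date is the start of the encounter rather than a specimen or result date, few admissions would precede it. Death, ventilation and the stay endpoints would still capture severe outcomes in these patients. Section 9.9 says that inferences about treatment or indication are not possible from the primary analyses.

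Part of this stands. The index-date convention could make the affected group small, and the size cannot be known from the protocol. It does not remove the point. Whether a stay in progress counts decides who has the event, so it is more than a code list. Section 9.7 itself sends major changes to primary endpoint definitions to a protocol amendment. A descriptive proportion must still count the patients it describes.

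A reader might infer more than the document supports:
- **That both primary endpoints plainly exclude patients already in hospital.** Only the ICU row names an admission, and no section states a scoring rule for such patients.
- **That the loss is larger for ICU than for hospitalization.** Nothing in the protocol shows this, and transfers to ICU after diagnosis work against it.
- **That the testing priorities establish a large inpatient-diagnosed share.** The list is described as in place on 22 April 2020, while the study period runs to 30 June 2022.
- **That this point overturns the Section 9.2.2 statement that "prescribed treatment regimens are not likely to determine probability of referral for testing".** That sentence goes on to make an exception for an association with symptomatic disease, and it is a separate matter.

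**Conclusion.** The point holds for the ICU endpoint on its literal wording: an ICU stay begun before the diagnosis date, without ICU readmission, is a No, while other endpoints in the same table count that stay. For hospitalization the finding is ambiguity. Two programmers could score the same patient differently and both follow the protocol.

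The size is unknown. The fall from 20% to between 16% and 8% rests on an assumed inclusive risk, assumed shares admitted first and no readmission. For hospitalization it applies only if the row is read as requiring a new admission. The relative loss equals the share of events admitted before diagnosis. The spurious ratio of 0.67 likewise shows what a modest difference in inpatient diagnosis could do; it does not estimate what happened. The baseline overlap holds unless the SAP carves out the index admission.

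This warrants a change to the definitions, because it concerns a primary endpoint and a severe group that the protocol itself foresees.

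**What to change.** 1. Define both primary endpoints to include a hospital or ICU stay that is open on the index date (the stay linked to the diagnosis) or that starts within 30 days after it. This aligns them with the stay-linked endpoints.
2. Use diagnosis site as a stratifier. Report both endpoints separately for patients diagnosed outside hospital, where the proportion is a true post-diagnosis risk.
3. For patients diagnosed during an admission, leave the pre-diagnosis days of that admission out of the baseline variables for days hospitalized and parenteral antibiotics.

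The cost is an amendment to the endpoint and baseline definitions and re-tabulation of existing data. Diagnosis site is already a study variable, so nothing new has to be collected. Counts will be smaller in the outpatient-diagnosed analysis and its intervals wider. Timing is tight: Section 6 dates the end of data collection 11 October 2022 and the final report 11 September 2023, 13 days after this version of 29 August 2023. The change may therefore have to appear as a re-analysis in or after the report.

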9.4. Data Sources

The structured data within Optum COVID testing database will be used to identify populations, exposures, confounders and endpoints of interest as described in Section 9.3.

As of 22 April 2020 the Optum COVID database currently includes 32,000 patients who have either been tested for COVID-19 or diagnosed with COVID-19 (regardless of positive/negative result). Refreshes of this data are delivered on a bi-weekly basis through September 2020 and on a monthly cadence from October 2020 – February 2021. This cohort includes details of a patient's office visit and/or hospital stay, including but not limited to: demographic, diagnosis, procedures performed, vital signs and other biometric measures, laboratory results, and prescriptions written and dispensed. All diagnosis data in this study will be obtained from structured data (via ICD-10-CM codes or ICD-9-CM codes where applicable). All drug treatment data will be pulled from prescription written, medication administration, and procedure tables when appropriate (via ICD-9-CM or ICD-10-CM, NDC, CPT, and HCPCS codes).

9.5. Study Size

Given the descriptive nature of most analyses, there is no minimum sample size. Sample size achieved will depend on the number of patients testing positive for SARS-CoV-2 and the indication-specific rate of infections and will increase over time with subsequent data cuts.

Prior to conducting any post-hoc comparative analyses, the feasibility of robust comparisons given accrued sample size will be assessed as described in the SAP.

9.6. Data Management

All study data exist as structured data by the time of study. Analyses will be conducted using SAS (version 9.4, SAS Institute, Cary, NC, USA). As the database will be regularly updated, date and version of the database will be specified in the report of the study, and the intermediate datasets will be archived if the report will be submitted to a regulatory agency or will be published.

9.7. Data Analysis

After selection of the study population, summary statistics of baseline variables will be determined for the baseline period. The index date for each patient is defined as the first date that the study inclusion criteria are satisfied. Baseline variables will be summarized as

appropriate for categorical and continuous variables with 95% CI provided to show precision of the estimate.

Among patients who are included in the study, outcomes will be included that occur during the risk window from index date until the first of death (based on discharge status), 3 months post-SARS-CoV-2 diagnosis, or end of study period/datacut.

The endpoints of interest within each indication, non-indicated subcohort and indication/treatment combination will be summarized as appropriate for categorical and continuous variables with 95% CI provided to show precision of the estimate.

The handling of missing data will be described in the SAP. No variables will be imputed.

Detailed methodology for summary and statistical analyses of data collected in this study will be documented in a Statistical Analysis Plan (SAP), which will be dated, filed and maintained by the sponsor. The SAP may modify the plans outlined in the protocol; any major modifications of primary endpoint definitions or their analyses would be reflected in a protocol amendment.

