8. RESEARCH QUESTION AND OBJECTIVES

The research questions that could be addressed by this study are:

What proportions of SARS-CoV-2 diagnosed patients have a diagnosis of RA, PsA, or UC (ie, indicated subcohorts) or not (ie, non-indicated subcohort) and what is risk of serious clinical manifestations and outcomes of interest in these subcohorts?

Within the indicated subcohorts of SARS-CoV-2 diagnosed patients, what is the proportion treated at baseline with the following systemic therapies: tofacitinib, JAK inhibitors, TNFi, non-TNFi, and csDMARD and what is risk of serious clinical manifestations and outcomes of interest within strata?

Primary objectives:

- Within subcohorts of SARS-CoV-2 diagnosed patients, determine the proportions of patients with a diagnosis of RA, PsA, and UC (indicated subcohorts) and patients without any of these conditions (non-indicated subcohort).
- For each indicated subcohort and non-indicated subcohort, describe baseline demographic characteristics, treatment history and comorbidities.
- Within each indicated subcohort and non-indicated subcohort, estimate proportion experiencing serious clinical manifestations and outcomes of interest (Section 9.3).
- Within each indicated subcohort of SARS-CoV-2 diagnosed patients, determine the proportions of patients treated with the following systemic therapies (class) at baseline: tofacitinib, JAK inhibitors, TNFi, non-TNFi and csDMARD (as monotherapy and combination therapy, as applicable).

- Describe patient characteristics, treatment history and comorbidities within baseline treatment strata.
- Estimate risk of serious clinical manifestations and outcomes of interest within baseline treatment strata (Section 9.3).
- Determine the proportions of patients that continue baseline treatment after SARS-CoV-2 diagnosis within indicated subcohorts.

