9. RESEARCH METHODS

9.1. Study Design

This is a retrospective cohort study involving secondary analysis of Optum administrative databases in the US consisting of longitudinal health information about patients tested for or diagnosed with SARS-CoV-2. The data source will be periodically updated and evaluated throughout the course of the study period.

The dataset consists of longitudinal data for patients from a subset of healthcare systems that expedite reporting of SARS-CoV-2 diagnoses, tests and their results. This dataset has been selected in the study in order to identify early insights into the potential risks of SARS-CoV-2 for indicated patients overall and by therapy.

This study is an active surveillance study consisting of repeat analyses over multiple timepoints, beginning with an 30 April 2020 data cut and repeated (summarized per status update as well as cumulatively) in order to understand the SARS-CoV-2 infected patients over time and across geographies as the virus spreads.

Any addition of post-hoc formal comparisons between groups will be described in a SAP pending feasibility based on sample size and data quality considerations.

This study period begins on 1 February 2020 and continues through 30 June 2022.

The study seeks to understand the serious clinical manifestations and outcomes of SARS-CoV-2 diagnosis among patients with RA, PsA, and UC and whether manifestations differ by treatment or by indication.

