9.2.3. Inclusion Criteria

Patients must meet all of the following inclusion criteria to be eligible for inclusion in the study:

- 1. SARS-CoV-2 diagnosis (as defined in SAP) (index date).
- 2. At least 6 months of continuous enrollment prior to index date.
- 3. Age 18 or older at index date.

For indicated subcohort:

1. Evidence of RA, PsA, or UC diagnosis (Section 9.3) within baseline period (to be defined in SAP) prior to index date.

For non-indicated subcohort:

1. No evidence of RA, PsA, or UC diagnosis (Section 9.3) within baseline period (to be defined in SAP) prior to index date

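### The Section 9.7 risk window does not end when a patient leaves observation, so early leavers count as non-events and fixed-horizon risks are understated

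*Protocol*

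**What the plan says.** Section 9.7 (Data Analysis) defines the period in which outcomes count: "outcomes will be included that occur during the risk window from index date until the first of death (based on discharge status), 3 months", continuing "3 months post-SARS-CoV-2 diagnosis, or end of study period/datacut". Three events end the window, and the sentence does not leave any further one to the SAP.

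Section 9.2.3 (Inclusion Criteria) requires "At least 6 months of continuous enrollment prior to index date". It sets no requirement after index, and Section 9.2.4 adds "There are no exclusion criteria for this study".

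Section 8 sets the target as a proportion: "estimate proportion experiencing serious clinical manifestations and outcomes of interest". Section 9.3 gives hospitalization as "Yes/No: hospitalization within 30 days post-SARS-CoV-2 diagnosis", ICU admission in the same form, and all-cause mortality as "Death within 90 days post-SARS-CoV-2 infection". Respiratory failure, kidney failure, thrombotic events, ARDS, heart failure and sepsis are diagnoses made in conjunction with the SARS-CoV-2 diagnosis, with no horizon of their own. Ventilation, ECMO, oxygen and immunoglobulin are tied to the associated hospitalization.

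On the data source, Section 9.1 says: "The dataset consists of longitudinal data for patients from a subset of healthcare systems". Section 9.7 leaves missing-data handling to the SAP and rules out imputation. Section 9.9 does not mention loss of observation after index.

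**The concern.** The protocol treats being observable as something it can define, since it requires it for six months before index. It then drops the idea at index. A patient who leaves the enrollment span a week after diagnosis can have no later event recorded, yet the window for that patient still runs to 3 months or the datacut.

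A Yes/No endpoint built from recorded events gives such a patient a No, and the patient stays in the denominator. The reported risk is then too low even for one group with no comparison in view. If completeness of observation differs between groups, part of any difference between the reported proportions reflects follow-up and not disease. That matters because Section 7 describes the aim as assessing whether tofacitinib modifies risk, and Section 9.1 asks whether manifestations differ by treatment or indication. Readers will set the strata side by side.

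**Working it through.** The protocol states no expected risk, exit rate or sample size, so there is no figure of its own to reproduce. The check has two parts.

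**1. Which endpoints are affected**

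| Endpoint (Section 9.3) | Horizon | Effect of leaving observation after index |
|---|---|---|
| Hospitalization, ICU admission (primary) | 30 days | Understated, by exits before day 30 only |
| All-cause mortality | 90 days | Understated, by exits before day 90 |
| Diagnosis endpoints (respiratory failure, sepsis and others) | None of their own; the 9.7 window applies | Understated, by exits within 3 months |
| Diagnosis site | Fixed at index | None |
| Procedures, in-hospital death, discharge disposition, lengths of stay | Associated admission | Largely none once that admission is observed |

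**2. How large the effect could be (illustration)**

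Assume a constant event hazard h and a constant exit hazard c over a horizon T, with exit unrelated to outcome. For true risk p and exit share L by T:

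- h = −ln(1 − p)/T and c = −ln(1 − L)/T
- simple proportion = h/(h + c) × [1 − exp(−(h + c)T)]

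All values of p and L are assumptions.

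*One group at 90 days, p = 10%:*

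| Share leaving by day 90 | Reported risk | Relative understatement |
|---|---|---|
| 5% | 9.75% | 2.5% |
| 10% | 9.50% | 5.0% |
| 20% | 8.98% | 10.2% |
| 30% | 8.44% | 15.6% |

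The relative understatement hardly changes for true risks between 2% and 20%. If all leavers exit immediately after diagnosis, the risk shrinks by the full share: 10% × (1 − 0.20) = 8.0%.

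*Two groups with equal true risk, 5% against 20% leaving over 90 days:*

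- Day 90, p = 10%: 9.75% against 8.98%, ratio 9.75/8.98 = 1.09.
- Exits by day 30 at the same rates: 1 − 0.95^(1/3) = 1.7% and 1 − 0.80^(1/3) = 7.2%.
- Day 30, p = 15%: 14.88% against 14.47%, ratio 14.88/14.47 = 1.03. It is also 1.03 for p = 5%, 10% or 20%.
- If the same shares leave immediately: 0.95/0.80 = 1.19 at either horizon.

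*Shares of events are not shares of patients.* Larger ratios come from assuming fractions of **events** unseen: 5% against 10% gives 0.95/0.90 = 1.06, 5% against 20% gives 1.19, and 10% against 30% gives 0.90/0.70 = 1.29. With exits spread evenly and a 30-day risk of 15%, leaving 20% of events unseen needs about 38% of patients to leave within 30 days, and 30% unseen needs about 54%.

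**The case against.** The strongest reply is that Section 9.7 says which outcomes count and nowhere says that unobserved patients are scored as event-free. It leaves missing data and detailed methodology to the SAP, which may modify the plan. It is true that counting leavers as non-events is an inference, and the SAP, which is not shown here, may add censoring. But the window itself is fixed in the protocol with three named ends, whereas Section 9.2.3 marks its baseline period as left to the SAP. A patient no longer observed leaves no record, which is not the same as a missing field. Followed as written, with simple proportions, the plan produces the non-event count.

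A reader might infer that every endpoint is biased low. Section 9.3 does not support that, because several endpoints are fixed at index or tied to the index stay.

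A reader might also infer that the indicated subcohorts will look worse because they are followed more closely. No section says that their observation after index is more complete. Section 9.9 notes that chronically ill patients may be more likely to be under ongoing care, but it raises this about care-seeking and testing. It also warns that differences between indicated and non-indicated groups may reflect access to care, and that inferences on treatment or indication are not possible. This limits the harm from a spurious contrast. It does not correct a proportion that is too low.

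Finally, censoring is not a full repair. Section 9.2.1 describes provider records and lists no enrollment span among its data elements. Care at a non-contributing hospital is missed even while the patient counts as enrolled. Death is taken from discharge status, so the competing event is itself incomplete. These points stand and shape the fix.

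**Conclusion.** The point holds in a limited form and should be acted on. Because the window in Section 9.7 has no end at loss of observation, and nothing is required after index, early leavers count as non-events. Hospitalization and ICU admission at 30 days, mortality at 90 days and the diagnosis endpoints without a horizon are understated; endpoints tied to the index visit or an observed index admission are largely unaffected.

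The size cannot be derived from the protocol, and neither can the direction of any difference between subcohorts. With evenly spread exits the distortion between groups is probably modest at 30 days: about 1.03 if 5% against 20% leave over 90 days, and about 1.09 at day 90. It reaches 1.19 for the same shares only if patients leave straight after diagnosis. All these figures rest on assumed exit rates and on exit being unrelated to outcome. The conclusion also depends on the SAP not already ending follow-up at loss of observation.

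**What to change.** - **Section 9.7, window:** add a fourth end, namely the end of the enrollment or observation span that is used to apply inclusion criterion 2.
- **Section 9.7, estimator:** estimate 30- and 90-day risks by a censoring-aware cumulative incidence (Aalen-Johansen), with death as a competing event for the non-fatal endpoints. At the least, give this as a sensitivity analysis beside the simple proportion, or repeat the proportion among patients observable through day 30 or day 90.
- **Tables:** report the percentage observed through day 30 and day 90, by subcohort and treatment stratum.
- **Section 9.9:** state that care and deaths outside the contributing systems remain unseen, and that censoring does not recover them.

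The follow-up span should not be ended at the last encounter, because encounter frequency depends on health.

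The cost is a clause in Section 9.7, a standard estimator, one extra row per table and a sentence in Section 9.9. The data already exist, so nothing new has to be collected. The downsides are slightly wider intervals and reliance on exit being unrelated to outcome, which is why the completeness figures should accompany the censored estimate.
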